8.3 Data handling, safety and quality assurance

The PI and study staff will be responsible for accurate and complete data collection.

The PI and the study staff will ensure that each subject's anonymity will be maintained and each subject's identity will be protected from unauthorized parties. The investigator will maintain all documents related to this study in strict confidence.

8.3.1 Source documentation

The PI and study staff will create case report forms (CRF) to record all study procedures and outcomes. CRF will be kept in binders dedicated to each subject upon enrollment. PI and study staff will keep all subject-specific materials in the subject binder. All general study related documentation such as study protocol, IRB communications, AE log etc. will be kept in the study binder.

8.3.2 Data safety

All collected data will be filed in study and subject binders. All binders are kept in the study coordinator's office which is locked. The office is located in a building with 24 hours security. Electronic data is not expected to be collected directly during the study except wound imaging. Wound imaging will be collected in a de-identified manner and stored on a secure server maintained by a vendor that is bound by US privacy regulations (See Appendix E). Data analysis will be conducted in a de-identified manner to ensure subject's confidentiality. None of the publications or presentations during and after study end will use any of the subject's personal identifier including images. If relevant, only non-identifiable images of wounds treated in the study will be used in future publications and/or presentations related to this study.

8.3.3 Data quality assurance

The PI and study staff will enter all data in the CRF in an accurate and complete manner. Regulatory personnel designated and authorized by the PI, Sponsor and IRB will periodically review all study materials for completeness and accuracy. They will produce a list of queries to the PI and study staff in order to resolve according the local Standing Operating Procedures.

8.4 Good clinical practice

The PI, study staff and the Sponsor are committed to ensure that all study procedures included in the protocol are carried out to the Good Clinical Practice guidelines set out by the International Conference on Harmonization. Additionally the PI, study staff and Sponsor are committed to abide by all legal requirements set by local agencies.

8.5 Study duration and premature termination

8.5.1 Each subject is enrolled in the study for eight weeks. It is anticipated that the study will be complete (i.e. last subject completed all eight weeks) within one year of first subject recruitment.

8.5.2 It is the intention of all parties to carry out the study to completion. However, if the PI, Sponsor, IRB or any other regulatory authority are made aware of any circumstances that suggest study subjects are at risk if the study continues, the PI or Sponsor, may decide on early termination of the study. Early termination decision will be taken in consultation between both PI and Sponsor.

CONFIDENTIAL

9 Appendices:

9.1 Appendix A - Molecular Microbiology Protocol ([name])

PURPOSE

The purpose of this protocol is to describe the methods that will be used to evaluate modifying bacterial load and silver resistance in samples from venous leg ulcers (VLU) subjects who have undergone standard of care treatment with Study Device (Cutimed® Sorbact®) and standard of care treatment with active control (Acticoat®) over a 4-week period. Genetic analyses (by qPCR) and standard microbiology will be utilized to characterize the mechanisms through which Cutimed® Sorbact® modifies bacterial load and promotes healing of chronic VLU. Understanding the mechanism through which Cutimed® Sorbact® stimulates healing in patients may promote, improve and expand its clinical use.

INTRODUCTION

The goal of the study will be to investigate the effect and mechanism of action of Cutimed® Sorbact® on bacterial populations and their silver resistance in VLU. Cutimed® Sorbact® products are BSN's proprietary technology dressing device for treating VLU.

Background and Rationale: Our previous *in vivo* studies utilizing porcine wound model have shown that silver treatment induces expression of virulence genes important for biofilm formation in clinical isolates of methicillin resistant *Staphylococcus aureus* and *Acinetobacter baumannii* [15]. Furthermore incidence of silver resistance is an emerging problem in treatment of chronic wound pathogens , [12].

Design: The study is multicomponent involving a clinical study guided by [name] and molecular laboratory component by [name].

The clinical study will enroll 30 patients with VLU who have been exposed to silver based therapy. Following a 2-week run-in phase, 15 subjects will be receiving Cutimed® Sorbact®, while other 15 subjects will receive common wound care product containing silver, Acticoat® in addition to standard of care (SOC). The treatment phase will last 4 weeks followed by a follow up visit 2 weeks later. The standard care involves weekly visits in which wounds will be cleaned and debrided. Debridement tissue from the wounds will be collected for molecular microbiological investigation.

Location: Subjects will be provided standard care at the UM dermatology clinical trials unit. The clinical team led by [name] is pursuing UM IRB approval. [name] and her team will conduct the molecular microbiology and standard microbiology assessments of the specimens collected in this exploratory patient outcome study.

RATIONALE

This research protocol will provide information that may further the understanding of Cutimed® Sorbact® treatment in accelerating wound healing via changes in microbial load and prevention of silver resistance. The bacterial load is increased in non-healing

VLU and promoting a non-healing wound phenotype. We will also evaluate expression of specific set of silver resistance genes whose expression may be stimulated by prolonged Ag-based therapy. [14]

Tissue Collection Procedure

Debridement tissue samples will be taken from the edge of the wound and will be taken at the initial visit and 2 additional points during the trial. The tissue will be transported in a sterile container on ice to [name] lab immediately after collection. One half of the tissue will directly stored into -80°C freezer for DNA isolation; the second half will be preserved in 80% glycerol for colony isolation using standard microbiology and analyzes of silver resistance on phenotypic level. The initial tissue removed will be considered the baseline and will be noted as T0.

Time Point Definitions

T0 – Pre-Randomization

T2 – Two weeks post-initial application SOC+ Cutimed® Sorbact® or SOC + Acticoat®

T3 – Three weeks post-initial application SOC+ Cutimed® Sorbact® or SOC + Acticoat®

DNA Isolation and qPCR

High bacterial burden ($>10^5$ organisms per gram of tissue), even without the classic signs of infection, is detrimental to healing [1, 10, 29]. Bacteria are routinely isolated from VLU by culturing methods. However, standard microbiology techniques present barriers to accurate microflora quantification because many of the chronic wound bacteria are recalcitrant to growth in a culture and are therefore difficult to identify in this manner [30]; [31]; [1]. The availability of molecular PCR based methods has provided researchers with the capability to examine the bacterial composition of human tissue samples in unprecedented detail. This approach would be utilized to further our understanding of mechanism of action Cutimed® Sorbact® on bacterial populations in VLU.

VLU debrided tissue will be collected from patients at the initial clinic visit (T0) and at routine follow-up visits (T2 and T3). Collected tissue will be measured and immediately after preserved at -80°C. DNA will be extracted from all samples using a solvent and grinding DNA extraction protocol (Bacterial/Fungal DNA isolation kit-Zymo Research). DNA quality and quantity control will be assessed by Real-Time PCR (qPCR) and Quant-It PicoGreen assay (Life Technologies), respectively. All of the methods required for DNA isolation and analysis are well established in [name] laboratory [32]; [33]; [34]. Quantification of all bacterial species in wound samples will be performed based on PCR amplification of 16S rRNA gene. The 16S rRNA gene (rDNA) is a DNA segment in all bacteria and archaea that codes for a structural RNA component of the small ribosomal subunit. The 16S rDNA is commonly used to quantify bacteria from human wound samples. We will employ 16S rDNA multiple hypervariable region to accomplish microbial quantification in VLU. Specifically, the 16S rDNA V1-V3 variable regions will be PCR

amplified to enrich the samples using the degenerate forward 27F.1 and non-degenerate reverse 518R primers that consist of sequences flanking the conserved hypervariable region. Separate PCR reactions will be prepared for each sample, including positive PCR control, and no template control. Real-time PCR will be performed and data will be analyzed using standard procedures established in [name] laboratory. Standard graphs will always be prepared from data accumulated at the same time as the test samples to act as internal controls. All qPCR reactions will be done in triplicate using the CFX96 real-time PCR system (Bio-Rad) and the PerfeCTa SYBR Green SuperMix (Quanta BioSciences). The relative CFUs will be calculated based on the standard curve. Assay results will be expressed as threshold cycle number (Ct) of the 16S rRNA gene copies per sample and tissue mass (mg). Standard curve will be used to determine relative CFUs based on Ct. Relative CFUs for tissue at two-weeks post initial treatment application (T2), and three weeks post treatment application (T3, if the percentage area reduction did not reach 75%). This qPCR based approach allows detection of bacteria which are difficult to cultivate and that would in all practicality remain undetected or underestimated by standard culture microbiology methods.

DNA standards for determining bacterial number by qPCR

Escherichia coli DNA is generally used as the standard for determining bacterial number by qPCR. However, to minimize the effect of variations in rDNA copy number on the calculation of bacterial number, DNA standards will be also prepared from two common VLU isolates, *Staphylococcus aureus* and *Pseudomonas aeruginosa*.

Detection of genes for resistance to silver

Resistance to silver compounds as determined by bacterial plasmids and genes has been defined by molecular genetics. Plasmid pMG101 is a 180-kb silver resistance plasmid that also confers resistance to several antibiotics. The possibility of the horizontal transfer and the increasing use of silver for wound dressing has raised concerns that bacterial resistance to silver might proliferate in a manner analogous to that seen for antibiotics and thereby compromise its clinical utility. The sil operon comprises nine ORFs, seven of which are apparently structural genes (silE, silC, silF, silB, silA, ORF105 and silP) and two of which (silR and silS) encode a putative two-component regulatory circuit. To date, only the function of SilE, SilP and SilS has been determined. SilE, functions as a periplasmic silver-binding protein by restricting the accumulation of silver in the cell through a combination of silver sequestration in the periplasm. SilP is responsible for active efflux as an ATPase transporter, and SilS encodes a regulatory circuit. For detection of these three silver resistance genes, a PCR method will be used. DNA isolated from all tissue samples collected at all time points will be screened for the silE gene silP and silS genes. This PCR base approach allows for detection of silver resistance even in bacteria that may not be grown using standard microbiology approach. Detection of genes encoding for silver resistance will be performed in batches from DNA isolated from 2 samples and more. *E. coli* strain ATCC 25922 (with the complete sil gene cassette) will be included as a positive control. The agarose gel electrophoresis of PCR products for silS, silE, and silP genes will be employed to confirm the expected size of the amplicons.

The PCR products will be confirmed by sequencing and the sequence will be analyzed for homology with the sil genes from pMG101 (NCIB Accession number AG067954) and *E. cloacae* Ag703 (NCIB 679159).

Susceptibility determinations and selection/phenotypic characterization of silver-resistant strains

Once we determine samples positive for the silver resistance genes we will further investigate whether the bacteria possessing Ag-resistant genes express this trait phenotypically. Bacteria will be isolated from the preserved glycerol stocks using standard microbiological methods (culturing on selective media). Tissue samples will be evaluated for the bacterial growth using microbiology methods. Culture condition will include both anaerobic and aerobic growth to enhance the level of bacterial detection. To recover bacteria serial dilutions from preserved stocks will be made from all tissue samples. The extent of microbiological colonization will be assessed using the Spiral Plater System. All plates will be incubated both aerobically and anaerobically at 37°C, after which the number of viable colonies will be counted. After the incubation period, colonies on the plates will be enumerated and the CFU/mL calculated. Similar methods have been used in our laboratories to evaluate the antimicrobial efficacy of various topical agents [33, 34]. All isolates will be tested for growth on LB agar supplemented with 250 µM Ag+ using patch method. Further Ag resistant phenotype will be confirmed for individual isolates using minimal inhibitory concentration (MIC) method.

MIC test to determine susceptibility to silver nitrate

The MIC of silver nitrate will be determined for all isolates capable of growing on LB agar supplemented with 250 µM Ag+. Bacteria will be suspended in Iso-Sensitest broth (Oxoid Ltd., USA). After an overnight incubation at 37°C, 10 µl of the bacterial suspension will be inoculated into a series of tubes with increasing concentrations of silver nitrate (4 to 512 mg/liter) in the same broth. The final bacterial concentration will be 105 CFU/ml. After 24 h of incubation, the MIC will be recorded as the lowest concentration yielding no visible growth. A silver nitrate MIC of >512 mg/liter will classify the bacterium as silver resistant. *E. coli* strain ATCC 25922 will be used as a control. Isolates confirmed for silver resistance will be preserved and further identification of bacteria on a species specific level will be proposed to sponsor.

Data Analyses and Reporting

qPCR Data will be analyzed using the software Prism (Graphpad, La Jolla, CA, USA). Raw data for qPCR will be provided to sponsor in txt format. All results including microbiology analyses, silver resistance and quantification of bacterial load will be presented in the final study report including analysis of data. PCR results will be expressed as threshold cycle number (Ct) of the 16S rRNA or silver resistance gene copies per sample and corresponding CFU/g tissue; the mean and standard deviation will be calculated for each time point. The longitudinal changes in bacterial load as

determined based on qPCR data analyses gene will be examined individually for each tissue. After counting the colonies for the MIC analyses, the data will be tabulated and the Log of colony forming units/g (Log CFU/g) determined. [name] will provide final results to include raw data.

CONFIDENTIAL

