Silver resistance: Silver (Ag) coated dressings are increasingly being used for chronic wounds based on bactericidal properties of released Ag, despite the lack of evidence to support their use [11]. Concerns of widespread Ag resistance in bacterial isolates from chronic wounds have been raised due to the increased utilization of silver based wound dressings [12] [13]. Silver resistant-strains have also been isolated from silver-treated patients at burn centers, where these stains have sometimes caused outbreaks [14]. Furthermore our *in vivo* studies utilizing porcine wound model have shown that silver treatment induces expression of virulence genes important for biofilm formation in clinical isolates of methicillin resistant *Staphylococcus aureus* and *Acinetobacter baumannii* [15]. Although the molecular basis for silver-resistance has been previously characterized [16] [14], to date, expression of silver resistance genes as a response to therapy has not been analyzed in clinical settings.

Here we propose to analyze the presence of silver resistance on genotypic and phenotypic level in response to treatment with Study Device (Cutimed® Sorbact®) and active control (Acticoat®).

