3. STUDY DESIGN

3.1 Overview:

This is an exploratory, single center, observer masked, active control, 1:1 randomized clinical trial. The goal is to compare the effectiveness of Study Device (Cutimed® Sorbact® wound contact layer) to an active control (silver contact layer Acticoat®). Both devices are already approved and indicated for treatment of wounds. Standard care selected for use in this trial includes sharp debridement and compression with Jobst Comprifore® 4 layer compression system.

The study consists of three phases: two weeks screening phase (phase-1), up to four weeks treatment phase (phase-2), and two weeks follow up phase (phase-3).

In the screening phase i.e. phase-1, the Investigators will choose Study Ulcer, make baseline measurements and assessments and verify inclusion and exclusion criteria are met. Standard care will be applied without use of Study Device or active control.

The treatment phase i.e. phase-2 may last up to four weeks (if healing did not occur prior) and includes application of study dressings as well as application of standard care and measurements of primary and secondary outcomes. This will be achieved by tissue collection procedures conducted at visits T0, T2, and T3. [name] and her research team will conduct the molecular microbiology and standard microbiology assessments of the specimens collected in this study. Gene expression (by qPCR) and standard microbiology will be utilized to characterize the mechanisms through which Cutimed® Sorbact® changes the bacterial load and promotes healing of chronic venous leg ulcers. Understanding the mechanism through which Cutimed® Sorbact® stimulates healing in patients may promote, improve and expand its clinical use.

In the two weeks follow up phase i.e. phase-3 subjects will return for one visit and secondary outcomes will be assessed and standard care provided. The subjects will then be discharged from the study and return to their wound care provider for further management as indicated.

3.2 Study outcomes:

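### Appendix A promises silver-resistance gene expression, but only DNA is assayed, so the trial can report gene carriage and abundance, not transcription

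*Combined protocol and SAP*

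**What the plan says.** **Where expression is promised or implied.** The Rationale of Appendix A states: "We will also evaluate expression of specific set of silver resistance genes", and adds that long silver treatment may stimulate that expression. The silver-resistance paragraph of Section 2 gives the motivation: "expression of silver resistance genes as a response to therapy has not been analyzed in clinical settings". Section 3.1 also uses the term: "Gene expression (by qPCR) and standard microbiology will be utilized to characterize the mechanisms". In 3.1, however, the mechanisms meant are those by which the device alters bacterial load and healing, and silver genes are not mentioned.

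**Where the aim is narrower.** Section 2 follows the gap with: "Here we propose to analyze the presence of silver resistance on genotypic and phenotypic level in response to treatment". The secondary outcome is described as genetic and phenotypic characterization in Sections 1 and 7, and as molecular and phenotypic in Section 3.2.2. The Purpose of Appendix A repeats the sentence from 3.1 almost unchanged but speaks of genetic analyses by qPCR.

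**What the laboratory does.** Under Tissue Collection Procedure: "One half of the tissue will directly stored into -80°C freezer for DNA isolation". The other half goes into glycerol for colony isolation and phenotypic testing. A DNA kit is used on all samples. For the silver genes: "DNA isolated from all tissue samples collected at all time points will be screened", the targets being silE, silP and silS, with confirmation by gel and sequencing. The Data Analyses and Reporting part of Appendix A then plans threshold cycles and gene copies per sample for both 16S and the silver resistance genes.

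**The concern.** Expression means transcription, and measuring it requires RNA. The Appendix A sentence is not a harmless synonym for carriage, because it refers to genes that silver therapy may stimulate, which is induction. If the wording stays, a change in a DNA signal between T0, T2 and T3 could be written up as induced or prevented expression, and the Section 2 gap described as filled.

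The DNA signal also has a problem of interpretation. The trial compares two dressings on bacterial load, so the arms may differ in load. A silver-gene result expressed per sample moves with load. An arm that removes more bacteria could show fewer positive samples or fewer sil copies with no change in the share of bacteria that carry the genes. Appendix A names prevention of silver resistance as a possible effect of the device, so such an artefact could be read as that benefit.

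**Working it through.** The plan gives no figure on this point, so there is none to reproduce. The check traces the stated analysis through the assay chain, then works through how the sil signal depends on load.

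**1. Assay chain (all in Appendix A)**

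| Step | What is described | Can it show transcription? |
|---|---|---|
| Tissue split | Half for DNA, half for glycerol culture | No aliquot is left for RNA |
| Extraction | DNA kit, all samples | No |
| 16S assay | qPCR on DNA | No, it measures load |
| sil assay | PCR on DNA for silE, silP, silS; gel and sequence check | No, it shows carriage |
| Reporting | Ct and gene copies per sample | No, it is DNA abundance |
| Phenotype | Isolates from glycerol stocks: growth on 250 µM Ag+ agar, then silver nitrate MIC | No, it shows the trait in culture |

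No section of the supplied text describes RNA preservation, RNA extraction, reverse transcription or a reference transcript. The culture step does ask whether carriers show resistance, but in isolates grown on laboratory media. It does not measure what the genes do in the wound under a dressing.

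**2. Dependence on load**

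Let N be the number of bacteria in the sample, p the share carrying a sil gene, a the sil copies per carrier and b the mean 16S copies per bacterium. Then:

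- sil copies = N × p × a
- 16S copies = N × b
- sil / 16S = p × a / b

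With p and a fixed, sil copies fall in proportion to N. For a fall of d log10 in load, copies fall 10^d-fold and the Ct rises by d × log2(10) = d × 3.32 cycles, assuming full PCR efficiency. The documents give neither an expected fall in load nor a sil detection limit, so the values of d below are assumptions:

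| Assumed fall d (log10) | Fold fall in sil copies | Ct shift (cycles) |
|---|---|---|
| 0.5 | 3.2 | 1.7 |
| 1 | 10 | 3.3 |
| 2 | 100 | 6.6 |

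A sample whose margin above the detection limit is smaller than this shift would turn from positive to negative with p unchanged. Dividing by tissue mass does not help, because N per gram is itself what the dressings are meant to change. In the ratio, N cancels. What remains is p scaled by a / b. Appendix A itself notes that rDNA copy number varies, so the ratio approximates the resistant share and does not measure it exactly.

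**3. Can the ratio be computed from the plan?**

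The detection section describes PCR with gel confirmation, which gives presence or absence. The reporting section plans Ct and copies for the silver genes, which requires quantitative PCR. Only the second yields a numerator, so the two sections must be reconciled first.

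**The case against.** The strongest reply is that this is loose wording, not a failed objective. The aim sentence in Section 2, the secondary outcome in Sections 1, 3.2.2 and 7, and the Purpose of Appendix A all ask for genetic or molecular and phenotypic resistance. The methods address that, and no analysis in Section 7 uses expression. This stands, and it limits the scope of the point.

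Three stronger readings are tempting, and the documents do not support them:

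- A reader might infer that the trial cannot answer its silver-resistance question at all. It can answer the listed one; only the expression analysis is out of reach.
- A reader might count Section 3.1 as a second promise about silver genes. That sentence concerns bacterial load and healing, so inserting sil genes there would be wrong.
- A reader might say the plan records gene presence only. The reporting section also plans silver-gene copies, and the culture work tests function. Both are useful, but neither measures transcription.

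It is also fair to say that the fold-change figures illustrate a mechanism and do not predict an effect, and that nothing in the plan commits the authors to reporting induced or prevented expression. The reply does not remove the Appendix A sentence, which commits the trial to an analysis that none of its assays can supply.

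**Conclusion.** The point holds in a limited form. The expression analysis stated in the Rationale of Appendix A, and framed by the gap in Section 2, cannot be delivered from DNA and cultured isolates. That follows from the described sample handling and needs no numerical assumption. The primary endpoint and the listed secondary outcome are untouched, so this should be corrected but does not threaten the trial.

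The load dependence is a matter of proportionality. How often it would change a result is unknown, because the detection limit, the sil copy numbers and the fall in load are not given. It would be an overstatement to say that the silver-gene comparison will be biased. What the documents support is that sil presence or copies per sample cannot by themselves separate a lower resistant share from a lower load.

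**What to change.** **Wording**

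- Appendix A, Rationale: replace expression with presence and copy number of silE, silP and silS.
- Section 3.1: replace gene expression with genetic analyses, the term already used in the Purpose of Appendix A.
- Section 2: state that this trial does not address the expression gap it describes.
- Limit conclusions to gene carriage or abundance and the culture/MIC phenotype.

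**Analysis**

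- Reconcile the detection and reporting sections of Appendix A by running the sil PCR as qPCR, keeping gel and sequencing as confirmation, and state its detection limit.
- Report sil copies relative to 16S copies from the same DNA, by arm and visit, beside presence/absence. Note that 16S copy number differs by species, so the ratio is only an approximate resistant share.

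**Cost.** The stated claim becomes narrower and a small amount of analysis is added. Quantitative sil PCR is already implied by the planned reporting of Ct and copies. If the sponsor does want expression, the alternative is an RNA workflow with its own tissue aliquot, reverse transcription, a reference transcript and a defined endpoint. That is a larger change, because all tissue is currently allocated.
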